9.1.4. PK Analysis Sets

The PK parameter analysis population is defined as all enrolled patients treated who have sufficient information to estimate at least one of the PK parameters of interest.

The PK concentration population is defined as all patients who receive PF-06801591, have no protocol deviations affecting the PK assessment, and have at least one post-dose concentration measurement.

9.1.5. Biomarker Analysis Set

The biomarker analysis set includes all enrolled patients with at least one of the pharmacodynamic/biomarker parameters evaluated at pre- and/or post-dose.

9.1.6. Immunogenicity analysis set

The immunogenicity analysis set is defined as patients who receive at least 1 dose of study treatment and have at least 1 ADA or NAb sample collected.

9.2. Statistical Methods and Properties

A primary study objective is to establish the MTD, defined as the dose that yields approximately 27.5% probability of DLT and considers equivalent doses that yield probability of DLT in the interval (equivalence interval) 22.5% to 32.5%. The 27.5% target, the symmetry of the equivalence interval and its upper limit <33% were chosen based on safety considerations. The prior distribution of DLT is set as a beta (0.5, 0.5), and the threshold probability for early termination and dose exclusion is set to 0.95. Doses with an incidence of DLT >33% (eg, 4 out of 10) will not be declared the MTD but will be allowed by the mTPI method.⁷

9.2.1. Dose Escalation/De-Escalation and MTD Estimation (Part 1)

Part 1 dose escalation phase of this study employs an mTPI design to estimate the MTD with the IV administration of PF-06801591. The mTPI design employs a simple beta-binomial model with prior a conjugated prior beta (0.5, 0.5). Decision rules are based on calculating the unit probability mass (UPM) of 3 intervals corresponding to underdosing, proper dosing, and overdosing in terms of dose limiting toxicity. A proper dosing interval is centered at the target toxicity rate (pT) of 27.5% with 5% uncertainty ($0.225 < pT < 0.325$). The under dosing interval is (0, 0.225), and the overdosing interval is (0.325, 1). The 3 dosing intervals are associated with 3 different dose escalation decisions. The underdosing interval corresponds to a dose escalation (E), overdosing corresponds to a dose de-escalation, and proper-dosing corresponds to staying at the same current dose. Given an interval and a probability distribution, the UPM of that interval is defined as the probability of the interval divided by the length of the interval. The mTPI design calculates the UPMs for the 3 dosing intervals, and the one with the largest UPM implies the corresponding dose-finding decision. That decision provides the dose level to be used for future patients. For example, if the underdosing interval has the largest UPM, decision E (to escalate) will be executed, and the next cohort of patients will be treated at the next-higher dose level. Under the mTPI design, a trial is terminated when either the lowest dose is above the MTD or a pre-specified maximum sample size of (for Part 1, n=60) is reached.

The following table shows the probability of escalating to the next dose level for a range of underlying true DLT rates. For example, for a cohort size of n=3 and for a DLT that occurs in 10% of patients, there is a greater than 90% probability of escalating. Conversely, for a DLT that occurs with a rate of 70%, the probability of escalating is 3%. It is assumed that dose escalation occurs with either 0/3 or 1/6 patients with DLTs.

Probability of Escalating Dose									
True underlying DLT rate	10%	20%	30%	40%	50%	60%	70%	80%	90%
Probability of escalating dose	0.91	0.71	0.49	0.31	0.17	0.08	0.03	0.009	0.001

9.2.2. Dose Expansion (Part 2: 300 mg of SC PF-06801591)

Part 2 (N=100) of this study is intended to further characterize the safety, efficacy, PK, PD, and immunogenicity profiles of 300 mg of SC PF-06801591 in anti-PD-1 or anti-PD-L1 treatment naïve patients with NSCLC (N=70) and urothelial carcinoma (N=30) who have progressed on or were intolerant to systemic therapy or for whom systemic therapy was refused or unavailable.

Summary statistics will be provided for trough PF-06801591 concentrations, safety endpoints, immunogenicity, pharmacodynamic/biomarkers, and efficacy data.

When the first 30 NSCLC patients have been enrolled and have either completed their first tumor assessment (at approximately 8 weeks post treatment), or have discontinued from the study before their first scheduled tumor assessment, preliminary assessment of safety and efficacy data maybe completed. This preliminary data may provide guidance in the decision to the increase or decrease size of each arm, to add other tumor types in a future amendment, or to initiate additional clinical studies.

9.3. Sample Size Determination

The exact sample size for the dose escalation design in Part 1 cannot be specified in advance due to the dynamic features of mTPI. For the first dose level (0.5 mg/kg IV), in the absence of actual DLTs, a total of 2 patients will be enrolled: 2 patients in Part 1A and no patient in Part 1B. For subsequent dose levels it is anticipated that approximately 2 to 4 patients will be enrolled in Part 1A and approximately 2 to 5 patients in Part 1B with available pre- and on-treatment biopsies for IHC testing and up to 9 patients at dose levels 1, 3, and 10 mg/kg administered by IV in Part 1. A single cohort with SC administration at a dose level of 300 mg of PF-06801591 will be opened for enrollment shortly after the cohort at a dose level of 3 mg/kg IV in Part 1A will have completed enrollment and the 21-day DLT observation period. This cohort at a dose level of 300 mg SC will seek 2 to 4 patients in Part 1A, up to 11 patients in Part 1B with available pre- and on-treatment biopsies for IHC testing, and up to 15 patients in Part 1. The actual Part 1 sample size may be smaller, depending on the underlying dose toxicity profile, and the number of dose levels studied.

Part 2 of the study will enroll approximately 70 patients with NSCLC who progressed on or were intolerant to systemic therapy or for whom systemic therapy was refused or unavailable. but are treatment naïve for anti-PD-1 or anti-PD-L1. NSCLC was selected for historical comparability to prior large anti-PD-1 studies and dosing of 300 mg SC in Part 2 has been selected based on safety, PK, available biomarker data and preliminary anti-tumor activity from Part 1. There is no hypothesis testing in Part 2. Estimation approach is used to characterize the precision of response data. The estimation of ORR using N=70 is described as follows. Suppose that the ORR estimate is 19% in Part 2 with N=70, then the 80% and 90% confidence intervals of the true ORR will be (13.4, 25.2%) and (12.2, 27.3%) respectively. Note that an ORR of 19% was observed in a clinical trial for nivolumab in previously treated NSCLC patients. In Part 2, approximately 30 urothelial cancer patients will also be enrolled; the sample size is based on clinical considerations of expanding the safety database.

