In a clinical research trial of 305 patients with no prior treatment for metastatic NSCLC with PD-L1 expression on greater than or equal to 50% of tumor cells, those who received pembrolizumab (200 mg q3w) had a significant improvement in PFS (HR 0.50 [95% CI: 0.37, 0.68]; $p < 0.001$) with a median PFS of 10.3 months versus 6.0 months for those receiving platinum-based chemotherapy. A pre-specified interim analysis demonstrated a statistically significant improvement in OS for patients randomized to pembrolizumab as compared with chemotherapy (HR 0.60 [95% CI: 0.41, 0.89]; $p < 0.005$). ORR was also significantly improved at 45% to 28%.

On October 24, 2016, the U.S. FDA approved pembrolizumab at a dose of 200 mg administered intravenously q3w for the treatment of patients with metastatic NSCLC whose tumors express PD-L1 on $\geq 50\%$ of tumor cells as determined by an FDA-approved test.

In KEYNOTE-042, pembrolizumab was compared with platinum-containing chemotherapy (carboplatin + paclitaxel or carboplatin + pemetrexed) in 1274 first line metastatic NSCLC patients, randomized 1:1 and analyzed in 3 different subgroups with 1-19%, $\geq 20\%$ and $\geq 50\%$ PD-L1 tumor proportion score (TPS). In the pembrolizumab arm subgroups, median survival in months were 16.7 (HR 0.81, 95% CI, 13.9 to 19.7), 17.7 (HR 0.77, 95% CI, 15.3 to 22.1) and 20.0 (HR 0.69, 95% CI, 15.4 to 24.9), respectively, whereas in the chemotherapy arm subgroups they were 12.1 (95% CI, 11.3 to 13.3), 13.0 (95% CI, 11.6 to 15.3) and 12.2 (95% CI, 10.4 to 14.2), respectively. Further exploratory analysis of this data revealed that dividing the patients in two groups with $\geq 1-49\%$ TPS revealed median OS of 13.4 months vs 12.1 months with HR of 0.92 (95% CI, 0.77 to 1.11) suggesting that survival benefit may be largely driven by the $\geq 50\%$ TPS group. As expected, pembrolizumab had better safety profile than chemotherapy except for immune-mediated adverse events experienced.⁴²

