1.2.7. Background Summary

This protocol is the first clinical study of PF-06801591 in patients with locally advanced or metastatic melanoma, SCCHN, ovarian cancer, sarcoma, NSCLC, urothelial carcinoma, or other solid tumors with clinical evidence of response to anti PD-1 or PD-L1 agents, who are unresponsive to existing therapies, or for whom standard treatment is not available. After preliminary determination of safe and effective exposure levels of PF-06801591 in Part 1 in

[figure not shown]
multiple solid tumor types, Part 2 will enroll two cohorts of NSCLC and urothelial carcinoma patients in order to evaluate whether the safety and efficacy of 300 mg SC PF-06801591 will be comparable to what has been seen with other approved anti-PD-1 agents intravenously in NSCLC and urothelial carcinoma.

Additional information for this compound may be found in the single reference safety document (SRSD), which for this study is the investigator's brochure.

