3. STUDY DESIGN

3.1. Study Overview

This is a Phase 1, open-label, multi-center, multiple-dose, dose escalation and expansion, safety, PK, and pharmacodynamic study of PF-06801591 in previously treated patients with locally advanced or metastatic solid tumor types with clinical evidence of response to anti PD-1 or PD-L1 agents. This clinical trial will include 2 parts: Part 1 dose escalation, and Part 2 dose expansion (see Figure 4). A total of approximately 140 patients will be enrolled into this study.

Figure 4. B8011001 Study Schematic

Part 1 will enroll patients with locally advanced or metastatic melanoma, SCCHN, ovarian cancer, sarcoma, NSCLC, urothelial carcinoma, or other solid tumor types with clinical evidence of response to anti PD-1 or PD-L1 agents. Patients will receive 0.5, 1, 3, or 10 mg/kg PF-06801591 intravenously (IV) every 3 weeks (q3w), or 300 mg PF-06801591 subcutaneously (SC) every 4 weeks (q4w).

Part 1 will be further divided into Part 1A (safety cohort) and Part 1B (pharmacodynamic cohort). For both IV and SC administration portions, each safety cohort will enroll 2-4 patients per dose level. For IV administration portion, each pharmacodynamic cohort will enroll 2 to 5 patients per dose level. For SC administration portion, up to approximately 11 patients will be enrolled into the 300 mg dose level in Part 1B. Approximately 40 patients will be enrolled into Part 1.

All patients in Part 2 will receive 300 mg PF-06801591 subcutaneously q4w. Part 2 dose expansion will include 2 arms: Arm 1 will enroll approximately 70 patients with NSCLC who progressed on or were intolerant to systemic therapy or for whom systemic therapy was refused or unavailable but have not previously received anti-PD-1 or anti-PD-L1. Arm 2 will enroll approximately 30 patients with urothelial cancer who progressed on or were intolerant to systemic therapy or for whom systemic therapy was refused or unavailable but have not previously received anti-PD-1 or anti-PD-L1. Approximately 100 patients will be enrolled into Part 2.

All patients:

1. Will undergo up to 4 weeks of screening prior to study entry.
2. Receive treatment with investigational product for up to 2 years, or until one of the following:
 - a. Disease progression by immune-related Response Evaluation Criteria in Solid Tumors (irRECIST, confirmed progressive disease [PD] or initial PD followed by rapid clinical deterioration), or
 - b. Unacceptable toxicity occurs, or

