4.1.2. Part 2 Dose Expansion

1. Either histological or cytological diagnosis of locally advanced or metastatic NSCLC or locally advanced or metastatic urothelial carcinoma who have progressed on or were intolerant to standard of care systemic therapy, or for whom standard of care systemic therapy was refused (refusal must be documented) or unavailable.
2. No prior treatment with anti-PD-1 or anti-PD-L1 therapy.
3. NSCLC patients whose tumor is not known to have anaplastic lymphoma kinase (ALK) or epidermal growth factor receptor (EGFR) mutation must not have received more than 1 line of prior systemic therapy and must have either:
 - a. Progressed on or after platinum-containing systemic therapy, or
 - b. Were intolerant to standard of care systemic therapy or
 - c. Refused standard of care systemic therapy (refusal must be documented).
4. NSCLC patients whose tumor is known to be ALK or EGFR mutation positive must have received prior systemic therapies that only include one or more lines of ALK or EGFR targeting drugs and chemotherapy limited to one line of a platinum-based regimen, and they must have progressed on or after both types of therapies.

5. Urothelial carcinoma patients must have received up to 2 lines of prior systemic therapy and either:
 - a. Progressed on or after platinum-containing systemic therapy, or
 - b. Were intolerant to platinum-containing systemic therapy, or
 - c. Had disease recurrence within 12 months of neoadjuvant or adjuvant treatment with platinum-containing chemotherapy, or
 - d. Were ineligible for platinum-containing systemic therapy, or
 - e. Refused standard of care systemic therapy (refusal must be documented).

If patients are treatment naïve and eligible for platinum-containing systemic therapy but are refusing platinum chemotherapy, they must also be documented to have previous PD-L1 high status as defined in the following table:

PD-L1 assay	Result	Threshold for PD-L1 High
Dako 28-8	TC	$\geq 5\%$
Dako 22C3	CPS	$\geq 10\%$
Ventana SP142	IC	IC $\geq 5\%$ and $< 10\%$ (IC2); or, IC $\geq 10\%$ (IC3)
Ventana SP263	TC, IC, ICP	TC $\geq 25\%$; or, ICP $> 1\%$ and IC $\geq 25\%$; or, ICP = 1% and IC = 100%

TC: Tumor cells
CPS: Combined positive score
IC: Immune cells
ICP: Immune cells present

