2. In the early data assessment, a Bayesian approach will be used to calculate the posterior probability that the true ORR is greater than or equal to the minimal expected ORR. For example, the minimal expected ORR if all patients received only one tumor assessment is approximately 10% but may be adjusted based on how many patients had assessments beyond 8 weeks and the PD-L1 status of patients which will be tested at baseline. A beta prior (0.235, 1) is chosen, where the parameter beta is set to be 1, and parameter alpha 0.235 was calculated from a reference product pembrolizumab on NSCLC patients where a 19% ORR was observed. For example, if 4 responders are observed out of the first 30 patients as of the first tumor assessments, the posterior probability that the true ORR is greater than a minimal expected ORR of 10% is approximately 70%.

3. When all 70 NSCLC patients and 30 urothelial cancer patients are enrolled and have completed their scheduled tumor assessments, another snapshot will be taken. Descriptive statistics (frequency and percentage) will be presented for each tumor type (NSCLC or urothelial cancer) for the following endpoints:
 - Tumor response (CR, PR, PD, SD etc.) at each assessment;
 - Best overall response up to week 16 (ie, across the first two tumor assessments plus the next consecutive tumor assessment when a confirmatory scan is needed);
 - Best overall response across all assessments;
 - ORR, the proportion of patients who achieved CR or PR, by week 16 and the 95% confidence interval for ORR;
 - DCR (disease control rate), the proportion of patients who achieved CR or PR or SD, by week 16 and the 95% confidence interval for the DCR.

If tumor response data are collected based on both RECIST 1.1 and irRECIST, separate presentations will be generated for each response criterion.

Time to event data (overall survival [OS], progression-free survival [PFS], time to response [TTR], time to progression [TTP], DOR, and duration of stable disease [DOSD]) will be analyzed by the Kaplan-Meier approach for each tumor type.

The analyses may be separated and performed at two separate time points if the 70 NSCLC and 30 urothelial cancer patients do not complete enrollment at approximately the same time.

4. A final analysis will be performed at the end of the study, which will be 2 years from LPFD.

Detailed analyses for these efficacy endpoints will be described in the Statistical Analysis Plan (SAP).

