6.2.3. ORR (Part 2)

ORR, as assessed using RECIST version 1.1 and irRECIST, is a primary efficacy endpoint for Part 2. The following analyses will be performed in the mITT population by tumor type (NSCLC or urothelial carcinoma) and pooled:

1. ORR by visit, separately for RECIST 1.1 and irRECIST: investigator provided tumor response CR, PR, and CR+PR will be presented by descriptive statistics (frequency and percentage) and 95% confidence interval.
2. Best overall response of CR, PR, and CR+PR, separately for RECIST 1.1 and irRECIST. This will include best overall response derivation without confirmation and with confirmation. Descriptive statistics (frequency and percentage) and 95% confidence interval will be provided.

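### Part 2 sets NSCLC response beside a 19% ORR from previously treated patients, but admits untreated patients and plans no ORR split by prior therapy

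*Protocol*

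**What the plan says.** **Aim and yardstick.** Protocol 1.2.7 says Part 2 will evaluate whether SC dosing gives safety and efficacy "comparable to what has been seen with other approved anti-PD-1 agents intravenously in NSCLC and urothelial carcinoma". Protocol 9.3 gives comparability with earlier large anti-PD-1 studies as the reason for choosing NSCLC, and adds "Note that an ORR of 19% was observed in a clinical trial for nivolumab in previously treated NSCLC patients". SAP 5.2.3 repeats this. Both sections state that Part 2 has no hypothesis test.

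**Who can enter.** Under inclusion criterion 3 in protocol 4.1.2, NSCLC patients without a known ALK or EGFR mutation "must not have received more than 1 line of prior systemic therapy and must have either" progressed on or after platinum, been intolerant of standard therapy, or (3c) "Refused standard of care systemic therapy (refusal must be documented"). Criterion 4 admits ALK- or EGFR-positive patients only after progression on both targeted drugs and platinum. Protocol 3.1 nevertheless describes the whole trial as a "pharmacodynamic study of PF-06801591 in previously treated patients with locally advanced or metastatic solid tumor types".

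**How ORR is reported.** Protocol 9.4 reports by tumor type. SAP 6.2.3 says: "The following analyses will be performed in the mITT population by tumor type (NSCLC or urothelial carcinoma) and pooled", where the pooling is across the two tumor types. The groupings in SAP 6.3.1 use only tumor type and dose.

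**Prior for the early look.** Protocol 9.4 and SAP 7 use a Beta(0.235, 1) prior, with 0.235 "calculated from a reference product pembrolizumab on NSCLC patients where a 19% ORR was observed".

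**The concern.** In a single-arm cohort, the comparison with outside results is only as good as the match between the populations. The 19% belongs to previously treated patients. The arm measured against it may also contain patients who have had no systemic therapy, and nothing in the plan limits their number or selects them by PD-L1. The urothelial arm is handled differently: untreated, platinum-eligible patients who refuse platinum must be PD-L1 high.

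If untreated patients respond more often, a drug or route that does worse than the benchmark after prior therapy could still show an all-NSCLC ORR near 19%. The NSCLC response data may guide arm size, added tumor types and new studies (protocol 3.1.2, 9.4). Protocol 3.1.8 makes the 300 mg dose the RP2D if efficacy and safety are confirmed in Part 2.

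**Working it through.** **1. The plan's own precision figure.** Protocol 9.3 supposes an ORR of 19% with N=70 and states an 80% CI of 13.4 to 25.2% and a 90% CI of 12.2 to 27.3%. A Wilson score interval for 13/70 (18.6%) gives 13.4 to 25.2% and 12.1 to 27.3%. The figures reproduce within 0.1 point, so the arithmetic is sound and the issue is the population behind the 19%.

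**2. Inputs for the case mix.**
- Benchmark: 19%, nivolumab, previously treated (protocol 9.3 and 1.2.5).
- Response in untreated patients: the only single-agent first-line anti-PD-1 ORR in protocol 1.2.5 is 45%, for pembrolizumab in patients with PD-L1 of at least 50%. No rate for unselected untreated patients is given; 30% is assumed as a lower alternative.
- Untreated share f: not given. Assumed range 10 to 50%.

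**3. Drug exactly equal to the benchmark in treated patients.** Expected all-NSCLC ORR = (1 − f) × 19% + f × p, where p is the ORR in untreated patients.

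| f | p = 30% | p = 45% |
|---|---|---|
| 10% | 20.1% | 21.6% |
| 20% | 21.2% | 24.2% |
| 30% | 22.3% | 26.8% |
| 40% | 23.4% | 29.4% |
| 50% | 24.5% | 32.0% |

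**4. Drug below the benchmark in treated patients.** Assume a true ORR of 12% in treated patients, about the lower 90% limit in protocol 9.3. The all-NSCLC rate reaches 19% when f = (19 − 12)/(p − 12):
- p = 45%: 7/33 = 21%.
- p = 30%: 7/18 = 39%.

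**5. A pull in the other direction.** Suppose 20% of the arm are ALK- or EGFR-positive patients under criterion 4 with an ORR of 5% (both assumed), 20% are untreated, and the remaining 60% respond at 19%:
- p = 30%: 0.60 × 19 + 0.20 × 30 + 0.20 × 5 = 18.4%.
- p = 45%: 0.60 × 19 + 0.20 × 45 + 0.20 × 5 = 21.4%.

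The upward shift shrinks and can vanish.

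**6. The prior.** Its mean is 0.235/1.235 = 19.0%. With 4/30 responders the posterior is Beta(4.235, 27) and P(ORR > 10%) = 69.0%, against about 70% stated. Section 1.2.5 gives pembrolizumab 29 to 30% in previously treated patients with PD-L1 of at least 1%. A prior mean of 29 to 30% would need alpha of 0.29/0.71 = 0.41 to 0.30/0.70 = 0.43, and the posterior becomes 72.0 to 72.4%. The choice of source hardly matters to the result.

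**The case against.** **No formal comparison exists.** Part 2 is estimation only. The 19% illustrates interval width, the early look uses about 10%, and RP2D confirmation names no ORR threshold. A reader might infer that the case mix inflates a false-positive rate or helps the drug past a responder cut-off. The documents contain no such test or cut-off. This stands, and it limits the harm to interpretation and to the decisions that draw on it.

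**The direction is not established.** A reader might take 45% against 19% as the effect of line of therapy. Those figures come from different drugs and different PD-L1 selection, and pembrolizumab reached 29 to 30% in previously treated patients. The documents cannot isolate a line effect, and step 5 shows an opposing influence. This also stands.

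**The pembrolizumab label may be right.** A reader might conclude that the 19% in protocol 9.4 and SAP 7 is really the nivolumab result. Section 1.2.5 gives 19% in NSCLC only for nivolumab, but 9.4 names no trial and another pembrolizumab source cannot be excluded. Only a query is supported.

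**Partial safeguards exist.** The early-look threshold may be adjusted for PD-L1 status, SAP 6.1 tabulates prior medication, and SAP 5.3 allows further exploratory analyses. None prespecifies ORR by prior therapy, so the core point remains.

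**Conclusion.** The point holds as a matter of matching populations. The all-NSCLC ORR describes a mix that may include untreated patients, whereas the cited 19% describes treated patients only, and no visible table separates the two. A shift upward is likely but not certain.

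Its size cannot be fixed from the documents. If the drug matched the benchmark in treated patients, the all-NSCLC ORR would be expected at about 20 to 32% over the assumed range, ignoring ALK- or EGFR-positive patients. If the true rate in treated patients were 12%, between 21% and 39% untreated would be enough to bring the total to 19%. These results rest on an assumed untreated share, on a 45% rate from PD-L1-selected patients and on an assumed 30%. They illustrate what could happen and do not predict it.

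This is a cheap improvement to an estimation-only cohort, not a flaw that invalidates its analysis.

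**What to change.** - **Main analysis (protocol 9.4, SAP 6.2.3).** Prespecify NSCLC ORR with an exact 95% CI in two groups: any prior systemic therapy for advanced disease, and none. The groups cover every patient and do not overlap: treated-but-intolerant patients fall in the first, and patients with adjuvant platinum only fall in the second. Read only the first group against 19%. Keep the all-NSCLC ORR as the main description.
- **Early look (SAP 7).** Keep the planned posterior in all 30 patients and show responder counts by the same split beside it. Restricting the posterior to a subset would discard information from an already small look.
- **Source query.** Ask the sponsor to identify the trial behind the 19% pembrolizumab ORR in protocol 9.4 and SAP 7.

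**Cost.** Wording in both documents and one extra split of an existing table. Treatment history is already collected under Tumor History in the Part 2 Schedule of Activities. The statistical price is precision: if 30% of the 70 patients were untreated, 49 would remain, and 9/49 gives an exact 95% CI of 8.8 to 32.0%, against 10.3 to 29.7% for 13/70. The treated group would still include ALK- or EGFR-positive patients, so the match with the benchmark improves but is not perfect.
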